4 OBJECTIVES AND OUTCOME MEASURES/ENDPOINTS

4.1 Primary objective

Determine the impact of reduced muscle lipid availability and increased glycolytic flux on forearm glucose uptake during short-term forearm immobilization in healthy volunteers.

Research question: Does lowering muscle lipid availability and increasing glycolytic flux attenuate the immobilization-induced decline in forearm glucose uptake?

Null hypothesis: Lowering muscle lipid availability and increasing glycolytic flux does not attenuate the immobilization-induced decline in forearm glucose uptake.

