9 STATISTICS AND DATA ANALYSIS

9.1 Sample size calculation

We have powered the study to detect a difference in forearm glucose uptake (primary outcome measure) between 1) Acipimox vs placebo, and 2) Salbutamol vs placebo. We have powered the study based on detecting differences in the change in forearm glucose uptake as measured during the hyperinsulinaemic-euglycaemic clamp, which is golden standard to measure insulin sensitivity. We have recently generated pilot data to demonstrate that forearm glucose uptake decreases by $13\pm 8\%$ (mean \pm SD) in response to mixed meal ingestion following 2 days of forearm immobilization. Based on our hypotheses, lowering lipid availability (via Acipimox) and stimulating glycolytic flux (via Salbutamol) will alleviate insulin resistance (i.e. prevent the decline in forearm glucose uptake). The following data were used to estimate the effect size, using $\alpha = 0.05$; power = 80%; significance = 5%:

- 1) Placebo ($-13\pm 8\%$) vs Acipimox ($0\pm 8\%$; preservation of forearm glucose uptake [14]. Effect size: 1.625. Required: $n=8$
- 2) Placebo ($-13\pm 8\%$) vs Salbutamol ($-4.3\pm 6\%$; 66% attenuation of decline in forearm glucose uptake by a beta2-agonist [28, 29]. Effect size: 1.23. Required: $n=12$

To have enough power for both comparisons, $n=12$ participants will be included in all groups (i.e. placebo, Acipimox, Salbutamol).

Thus, assuming a $\leq 20\%$ dropout rate (in our experience, similar immobilization studies do not exceed this drop-out rate when using healthy adults), we will recruit 45 healthy adults 18-40 years old, from both sexes, who will be split across 3 parallel groups (i.e. $n=15$ per group, ensuring completion of $n=12$ per group).

Sample size was calculated using G*Power 3.1.9.2.

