9.3.2 Primary outcome analysis

The primary outcome measure for this study is forearm glucose uptake, measured during the steady-state phase of a 3-h hyperinsulinaemic-euglycaemic-hyperaminoacidaemic clamp. A two-way ANOVA, with and treatment (placebo vs Acipimox vs Salbutamol) as between-subjects factor and time (pre vs post immobilization) as within-subjects factor. A Bonferroni post-hoc test will be used to locate individual differences.

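### The primary analysis does not carry forward the two drug-placebo comparisons of change that the trial is sized on, so the result that decides each drug is left open

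*Combined protocol and SAP*

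**What the plan says.** - Section 4.1 gives a single null for two mechanisms that are tested in different arms: "Lowering muscle lipid availability and increasing glycolytic flux does not attenuate the immobilization-induced decline in forearm glucose uptake". No arm receives both drugs. The section does not say whether success of one drug is enough to reject this null.
- Section 9.1 is more specific. The trial is powered for a difference "between 1) Acipimox vs placebo, and 2) Salbutamol vs placebo", and the quantity compared is stated as "detecting differences in the change in forearm glucose uptake". Each comparison has its own effect size and its own n at 5% significance and 80% power. The larger n, 12 per group, is used for all arms.
- Section 9.3.2 specifies a two-way ANOVA with treatment (three levels) between subjects and time (pre, post) within subjects, and then: "A Bonferroni post-hoc test will be used to locate individual differences". It does not mention the interaction, the two comparisons of 9.1, the set of comparisons that Bonferroni covers, or whether the post-hoc step depends on a prior significant F test.
- Section 9.3.3 applies the same analysis to muscle protein synthesis and nutrient balance.

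**The concern.** Attenuation of a decline is a difference between a drug arm and placebo in the change from pre to post. In a 3 x 2 design that is a treatment-by-time contrast. A post-hoc test after such an ANOVA is ordinarily run on the six cell means, and so compares pre with post within an arm or compares arms at one visit. Neither estimates a difference in change. The interaction F test does address change, but with three arms it does not say which drug worked.

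The within-arm version invites the inference that a drug preserved uptake because placebo fell significantly and the drug arm did not. That compares two significance results, not two groups. If the analyst may choose among these readings after seeing the data, the verdict on a drug can depend on the choice, most of all for Salbutamol, where a partial effect is expected.

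**Working it through.** **Reproducing section 9.1** (two-sample t test, two-sided 5%, 80% power, noncentral t).
- Acipimox: d = 13/8 = 1.625, n = 8 per group.
- Salbutamol: d = (13 − 4.3)/√((8² + 6²)/2) = 8.7/7.07 = 1.23, n = 12 per group, power 82.1%.
- Recruitment: 3 × 12/(1 − 0.20) = 45.

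All three agree with the plan. They confirm that the sizing is for two separate, unadjusted drug-placebo comparisons of change.

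**Rules compared** (simulation, 12 per arm, ANOVA error pooled over arms).
- Contrast rule: drug minus placebo difference in change, Bonferroni over 2.
- Within-arm rule: placebo decline significant and drug-arm decline not, Bonferroni over 3. The plan does not state this rule; it is one reading of the post-hoc step. It is run ungated, and also gated on a significant interaction.

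**At the effects in 9.1** (−13±8, 0±8, −4.3±6).

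| Result | Share of trials |
|---|---|
| Interaction F significant | 96% |
| Contrast rule: Acipimox / Salbutamol succeeds | 96% / 71% |
| Within-arm rule: Acipimox / Salbutamol succeeds | 99% / 71% |
| Rules disagree for at least one drug, ungated | about 32% |
| Rules disagree for at least one drug, gated | about 29% |
| Rules disagree for Salbutamol, ungated / gated | about 30% / 27% |

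For Salbutamol both rules succeed in about 71% of trials, yet they disagree in 30%. Since the success rates are almost equal, the disagreement must split about evenly, near 15% each way. The two rules therefore declare success in partly different trials.

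At least one contrast succeeds in 97% of trials and both succeed in 70%, so in 97 − 70 = 27% exactly one drug succeeds and the joint null in 4.1 has no stated verdict.

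Comparing arms only at the post visit is weak. With Bonferroni over 3, power is 52% / 22% (Acipimox / Salbutamol) if the baseline SD is assumed to be 10% of the mean, and 17% / 7% if it is 20%. The plan gives no baseline SD.

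**With no drug effect.** If p is the power of one arm's pre-post test, the ungated within-arm rule errs for either drug with probability of about p(1 − p²). At −13±8 the noncentrality is 13√12/8 = 5.63, so p = 0.9986 and the error is 0.9986 × (1 − 0.9972) = 0.3%. The expression peaks at p = 1/√3, where it is 38.5%.

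| Common decline (mean±SD, %) | Source | Within-arm rule, ungated (simulated) |
|---|---|---|
| −13±8 | section 9.1 | 0.3% |
| −10±8 | assumed | 7% |
| −8±8 | assumed | 25% |
| −6.5±8 | assumed | 36% |
| −13±16 | assumed | 36% |

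The gated rule errs in at most about 3% throughout. The contrast rule stays at about 2.3%.

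**If only Acipimox works** (fully preserving uptake), gating protects less, because the interaction is then often significant for a true reason. A false Salbutamol claim under the gated rule occurs in 0.1% of trials at −13±8, but in up to about 10% under the assumed declines. Under the contrast rule it is 0.025/2, about 1.2%.

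**The case against.** The strongest reply is that the intent is clear. Section 9.1 names both comparisons and the change measure, section 4.1 asks about attenuation, and only the interaction in the specified ANOVA addresses that. At the planned effects the interaction test and the contrasts (at least one significant) disagree in about 1% of trials. Section 9.3.2 does not define its individual differences, so contrasts of change are compatible with its wording. Much of this stands: the plan does identify the intended comparisons, and 9.1 largely answers whether one drug or both must succeed. But a sample-size rationale is not a decision rule, 9.3.2 does not refer back to it, and the interaction test alone gives no verdict per drug.

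A reader might also infer that the plan carries a 25–36% risk of falsely declaring attenuation. The documents do not support that. Those rates need an ungated within-arm rule that appears nowhere in the plan, and a smaller or noisier decline than 9.1 assumes. Nor does anything suggest that the investigators would claim drug benefit from the time main effect or from whichever of the three F tests is significant, so error rates for those rules say nothing about this trial.

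**Conclusion.** The point holds as a mismatch between sections 4.1, 9.1 and 9.3.2: the comparisons that the trial is powered for are not named as the tests that decide it. On the plan's own inputs, a plausible reading of the post-hoc step changes the verdict for at least one drug in about 32% of trials, or 29% with gating. This rests on 12 completers per arm, normally distributed changes and the ANOVA's pooled error.

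False attenuation is a smaller matter on those inputs: about 0.3% at −13±8 with no drug effect. The higher figures are sensitivity results. They merit attention because the pilot decline was observed "in response to mixed meal ingestion following 2 days of forearm immobilization", whereas the primary outcome is measured during a clamp, so the planned mean and SD may not transfer. The point should be corrected before analysis; it does not undermine the design.

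**What to change.** - In 4.1, replace the joint null with two, one per drug: the drug does not alter the pre-to-post change in forearm glucose uptake relative to placebo. Each has its own conclusion.
- In 9.3.2, state that each null is decided only by its drug-placebo treatment-by-time contrast (the difference in change), with Bonferroni over the two. State that main effects, within-arm pre-post tests and single-visit comparisons are descriptive and cannot support a claim of attenuation. Because 9.3.3 refers back to this analysis, the secondary outcomes follow.
- In 9.1, restate power at two-sided 0.05/2 = 0.025 per contrast: with 12 per arm and a two-sample test, about 93% for Acipimox and about 73% for Salbutamol, against 82% unadjusted.

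The cost is wording plus an openly lower Salbutamol figure. Section 9.3.2 already commits to Bonferroni, so most of that loss is implied now; over all three pairs of arms, Salbutamol power would be 66%. Reaching 80% with two contrasts would take 14 completers per group, which is 14/0.8 = 17.5, so 18 per group and 54 recruited. Restating the figure is preferable to enrolling more: if all 15 per group complete, simulated Salbutamol power is about 82%. The investigators also give up reporting a significant fall in placebo alone as evidence of drug benefit.

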9.3.3 Secondary outcome analysis

Secondary outcome measures include postabsorptive and postprandial muscle protein synthesis, and forearm branched-chain amino acid and fatty acid balance. These data will be analysed in the same way as the primary outcome described above.

9.3.4 Procedure(s) to account for missing or spurious data

The study will be designed to a high level of rigour, and processes will be methodically applied to minimise the occurrence of missing data. Where data are missed due to participant error / non-compliance or technical error, there will be a follow up investigation carried out by the research team try to locate the data, or, failing that, to optimise future data collection. If data are missed due to researcher error or technical failure, then this will be recorded on data sheets available to the research team at all times. Missing data analyses will be carried out using a commercial statistical analysis package (GraphPad Prism 7.03).

10 DATA MANAGEMENT

10.1 Source data and documents

All source data and source documents collected during the trial will be retained to allow subsequent reconstruction and evaluation of the trial. Researchers will ensure that all source data and documents are accurate, legible, complete and consistent to allow verification of the process for the purposes of confirmation, quality control and audit. Personal details will be stored up to a period of 5 years from the completion of the study, as we would like to store the personal details at least in line with the storage of blood samples to allow maximum data generation from the study performed.

[name] will act as custodian, and only her and [name] will have access to the source data. All members of the research team will comply with the Data Protection Act 1998 with regards to the collection, storage, processing and disclosure of personal information and will uphold the Act's principles.

Trial conduct may be subject to systems audit of the Trial Master File (TMF) for inclusion of essential documents; permissions to conduct the trial; Trial Delegation Log; CVs of trial staff and training received; local document control procedures; consent procedures and recruitment logs; adherence to procedures defined in the protocol (e.g. inclusion / exclusion criteria, correct randomisation, timeliness of visits); adverse event recording and reporting; accountability of trial materials and equipment calibration logs.

10.2 Data areas and data types

The research data to be managed are principally quantitative in nature obtained from investigation of healthy young male and female participants (18-40) e.g. screening data (height, weight, BMI, age, blood clinical chemistry, blood pressure, forearm volume etc.), habitual diet, body composition and muscle mass obtained from BodPod, and muscle protein synthesis rates and plasma tracer enrichments and/or amino acid and fatty acid concentrations of the collected blood samples. A proportion of the data will be qualitative (e.g. screening and physical activity questionnaires and diet diaries).

10.3 Standards and metadata

In compliance with UK Data Protection Laws, subject identifiable data (screening data, consent forms and screening questionnaires), and all hard copies of lab notebooks and documents will be kept in a locked room within the Clinical Research Facility (RILD building, RD&E site), specifically dedicated to storage of identifiable data. Once enrolled into a study, participants are assigned a subject number and research data generated incorporate this subject number as an identifier, i.e. no direct link to participant identity is used. Encrypted and password-protected electronic copies of these data will be made to ensure against the risk of loss. All members of the research team have relevant expertise of information security; having received training within the host institution.

All forms of experimental data will be collected electronically onto computer hard drives intrinsic to the equipment being used to make the measurement in question (e.g. mass spectrometer). Sufficient storage space is available on each system to allow adequate storage of large raw data, but all data will be backed up onto the project specific computer. Where possible the project will use open or widely used data formats and files. Electronic data will subsequently be stored on University managed network drives, featuring data backup and redundancy systems, with access rights to the storage area restricted to key personnel. Each researcher is allocated up to 100GB of secure, backed up network storage. Any data stored on the CI's computer will be backed up daily to an encrypted external hard drive, stored in a geographically different location, before being transferred to the network drive at the earliest opportunity. Good laboratory practice (GLP) will be applied throughout the project in the acquisition, management and archiving of study data. In compliance with the ICH/GCP guidelines, regulations and in accordance with the University of Exeter Research Ethics, the Chief Investigator will maintain all records and documents regarding the conduct of the study. All data will be retained for a period of at

least five years after completion of the project. If the responsible investigator is no longer able to maintain the study records, a second person will be nominated to take over this responsibility.

10.4 Methods for data sharing

The sponsor and investigators are fully committed to share data in accordance with the HRA Policy. High volume data generation is not a feature of the proposed project, and so the data will be predominantly disseminated via publication in high-impact peer-reviewed journals (within 12 months of study completion) and via presentation at conferences. Publications will be in accordance with the University of Exeter's Open Access policy and where possible immediately made openly available to adhere to the funder's policy. All data published and/or shared will be anonymized to prevent subject identification. Importantly, on request we will make available our primary data to external researchers, subject to preservation of intellectual property and written acknowledgement that data ownership will reside with the research team. While it is not anticipated, data that is not included for publication but may be of value to the research community will be archived in the University's Institutional Repository, Open Research Exeter (ORE). All data will be deposited and will be citable using a persistent identifier.

10.5 Proprietary data

The results generated from this study will give insight in the role of fuel integration during inactivity, as well as identify potential molecular treatment targets which could be of interest to major Pharma companies who currently have exciting programs around preventing muscle wasting. The University of Exeter Innovation, Impact and Business (IIB) team can help with industrial liaison and knowledge transfer, from IP protection to finding a company interested in the research outputs.

11 ETHICAL AND REGULATORY CONSIDERATIONS

11.1 Research Ethics Committee (REC) review and reports

The study will be conducted in compliance with the principles of the Declaration of Helsinki (1996), the principles of GCP and in accordance with all applicable regulatory requirements. Local ethical approval was obtained from the University of Exeter's Sport and Health Sciences Ethics Committee (please see attached certificate of ethical approval). This application is now submitted for REC approval as part of the Clinical Research Network portfolio adoption process, so that the RD&E Pharmacy can be accessed for dispensing of the drugs.

Before the start of the study, approval will be recognised from a REC for the study protocol, informed consent forms and any other relevant documents. Substantial amendments that require review by REC will not be implemented until the REC grants a favourable opinion for the study. All correspondence with the REC will be retained in the Trial Master File. The Chief Investigator will submit an annual progress report (APR) to the REC within 30 days of the anniversary date on which the favourable opinion was given, and annually until the study is declared ended. The Chief Investigator will notify the REC of the end of the study, and if the study is ended prematurely, the Chief Investigator will notify the REC, including the reasons for the premature termination. Within one year after the end of the study, the Chief Investigator will submit a final report with the results, including any publications/abstracts, to the REC.

11.2 Peer review

The scientific quality of this research has been assessed within the research team and CI's host institution, before submitting this as part of the CI's application for a Sir Henry Wellcome Postdoctoral Fellowship. The Fellowship application process consisted of two rounds of written submissions (please find reviewers comments from 3 independent expert reviewers included in this application) and an interview round with the Wellcome Trust's Basic Science Panel, consisting of approximately twenty panel members from various UK institutions. [name] was awarded this 4-year Fellowship in November 2017.

11.3 Indemnity

The University of Exeter has expanded its standard indemnity cover with an extra medical malpractice extension, specifically for this study (please see documents attached). This ensures that [name], whose activity on this study is not covered by the NHS indemnity scheme, is fully covered in his role of medical collaborator. This insurance covers the potential harm to participants arising from the management, design, and conduct of the research.

12 DISSEMINATION POLICY

The current proposal aims to conform to the principles of the 'European Charter for Researchers' by guaranteeing that the novel knowledge generated by the study is disseminated in a way that can be understood by the general public. The primary goal of these efforts is to distribute the key findings to the society and its affected individuals, as well as to health departments, policy makers, researchers, and health advocacy groups. The main mediums of communication and information dissemination are:

- 1) Peer-reviewed journal article(s). Data will be published in peer-reviewed journals according to RCUK/HEFCE guidelines, with gold or green access. The data will be published as one or more journal articles, depending on the outcomes of the study.
- 2) A project website that will be launched to inform the general public on the objectives, funding body, conclusions, and general recommendations of the project.
- 3) Social media such as specifically created Twitter and Facebook pages as well as my personal Twitter account. Data will also be shared via ResearchGate.com, where a project page for this study will be set up.
- 4) Local events. Examples of these are Soapbox Science, which showcases research of women who are making significant contributions to the scientific community, and Pint of Science, a festival which allows scientists to discuss their research with the general public in a local pub.

